5.6.3 Laboratory Values

Laboratory values that are nonmissing and reported as “below the detectable limit” of an assay will be replaced by half the detectable limit in the summary tables. Laboratory results will be summarized using Système International (SI) units. Laboratory test results will be assigned a low/normal/high (LNH) classification according to whether the value was below (L), within (N), or above (H) the laboratory parameter’s reference range. Abnormal laboratory values will be identified as those outside the normal range. The abnormal values will be indicated in data listings. The CTCAE grade will also be included in the listing.

Laboratory tests during treatment are defined as laboratory tests conducted from the start of treatment to no more than 28 days after the last dose of study drug. Only laboratory parameters specified in the protocol will be summarized. Other laboratory parameters collected for some individual subjects will be presented in listings only. Baseline is defined as the last nonmissing result prior to the first administration of study drug.

For quantitative parameters, the actual value and the change from Baseline to each postbaseline visit will be summarized by visit and dose level (Phase 1)/study cohort (Phase 2) using descriptive statistics. Qualitative parameters will be summarized using frequencies (number and percentage of subjects), and changes from baseline to the worst postbaseline will be reported using shift tables. Percentages will be based on the number of subjects with both nonmissing baseline and relevant postbaseline results.

5.6.3.1 Hematology and Clinical Chemistry

Laboratory parameters will be reported using the following methods for hematology and clinical chemistry:

- Descriptive summary statistics for all major hematology and clinical parameters and their changes from Baseline will be calculated (n, mean, SD, median, Q1, Q3, min, max)
- Shifts from Baseline to worst postbaseline CTCAE grade (presented by each dose level in Phase 1 and overall, and each study cohort in Phase 2) for all clinical chemistry parameters and hematology parameters.

All hematology and clinical chemistry laboratory parameters will be listed by subject and visit.

5.6.3.2 Thyroid-Stimulating Hormone

Thyroid-stimulating hormone values will be summarized separately at both Baseline and for worst postbaseline value in 2 categories (\leq ULN and $>$ ULN).

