9.5.1.5.1 ADVERSE EVENTS

An AE is any untoward medical occurrence in a patient or clinical investigation subject administered an investigational product. An AE does not necessarily have a causal

relationship with the medicinal product. For this study, the study drugs are lenvatinib and everolimus.

The criteria for identifying AEs in this study are:

- Any unfavorable and unintended sign (including an abnormal laboratory finding), symptom, or disease temporally associated with the use of an investigational product, whether or not considered related to the investigational product (Note: Every sign or symptom should not be listed as a separate AE if the applicable disease [diagnosis] is being reported as an AE)
- Any new disease or exacerbation of an existing disease. However, worsening of the primary disease should be captured under efficacy assessments as disease progression rather than as an AE.
- Any deterioration in nonprotocol-required measurements of a laboratory value or other clinical test (eg, ECG or x-ray) that results in symptoms, a change in treatment, or discontinuation of study drug
- Recurrence of an intermittent medical condition (eg, headache) not present pretreatment (Baseline)
- An abnormal laboratory test result should be considered an AE if the identified laboratory abnormality leads to any type of intervention, withdrawal of study drug, or withholding of study drug, whether prescribed in the protocol or not.

All AEs observed during the study will be reported on the CRF. All AEs, regardless of relationship to study drug or procedure, should be collected beginning from the time the subject signs the study ICF through the last visit and for 28 days after the last dose of study treatment. Serious AEs (SAEs) will be collected for 28 days after the last dose of study treatment.

Abnormal laboratory values should not be listed as separate AEs if they are considered to be part of the clinical syndrome that is being reported as an AE. It is the responsibility of the investigator to review all laboratory findings in all subjects and determine if they constitute an AE. Medical and scientific judgment should be exercised in deciding whether an isolated laboratory abnormality should be classified as an AE. Any laboratory abnormality considered to constitute an AE should be reported on the Adverse Event CRF.

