- Incidence and Time to First Onset of CSAEs for lenvatinib and AEOSI for everolimus

The following tables will be provided only for subjects in Phase 1.

- TEAEs in Cycle 1 in decreasing frequency of PT
- TEAEs in Cycle 1 by SOC and PT
- TEAEs in Cycle 1 with CTCAE Grades ≥ 3 by decreasing frequency of PT

The following subject AE listings (treatment-emergent or otherwise) will be provided:

- All AEs
- All deaths for all enrolled subjects
- All SAEs
- All AEs leading to study drug discontinuation
- All AEs leading to dose reduction and / or dose interruption
- Subjects with Febrile Neutropenia
- All CSAEs

The following subject listings will be provided only for subjects in Phase 1.

- DLTs in Cycle 1
- TEAEs in Cycle 1

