5.6.3.3 Urinalysis

The shift of Baseline to worst postbaseline proteinuria will be summarized. All urinalysis parameters (RBCs/high-power-field [HPF], blood, glucose, and protein [dipstick], 24-hour urine protein) will be provided by subject listing at each visit.

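### The planned TSH table gives baseline and worst postbaseline categories separately, so it does not show how many subjects rose above the ULN on treatment

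*SAP*

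**What the plan says.** SAP section 5.6.3.2 is a single sentence: "Thyroid-stimulating hormone values will be summarized separately at both Baseline and for worst postbaseline value in 2 categories". The two categories are at or below the ULN and above the ULN. No shift table or cross-tabulation is mentioned.

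The sections around it do specify baseline-to-worst comparisons:

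- Section 5.6.3.1, for hematology and clinical chemistry: "Shifts from Baseline to worst postbaseline CTCAE grade".
- Section 5.6.3.3, for urinalysis: "The shift of Baseline to worst postbaseline proteinuria will be summarized".
- Sections 5.6.3.4, 5.6.3.5 and 5.6.4 do the same for height and blood pressure percentiles, ECG findings, and Lansky or Karnofsky scores.

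Thyroid function is tested every cycle, and TSH sits in the Chemistry block of the laboratory table (Protocol section 9.5.1.5.3, Table 6). SAP section 5.6.2 names hypothyroidism as a clinically significant adverse event (CSAE) for lenvatinib.

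**The concern.** A reader will bring one main question to a TSH table in a lenvatinib study: how many children with TSH at or below the ULN at entry went above it on treatment? In a single-arm study each subject's own baseline is the natural reference. Two one-way summaries give the margins of the two-by-two table and leave out its cells. The proportion above the ULN at worst postbaseline mixes new elevations with elevations already present at entry.

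The two can differ only if some subjects enter above the ULN. Nothing in the inclusion or exclusion criteria (Protocol sections 9.3.1 and 9.3.2) prevents that. Phase 2 also admits subjects with up to two prior VEGF/VEGFR-targeted therapies (inclusion criterion 4k), so pre-existing elevation is plausible. That is an inference; the documents give no frequency.

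What is at stake is how well one descriptive safety table can be read. No objective, endpoint or decision rule uses a TSH-elevation rate.

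**Working it through.** The plan states no figure here to reproduce. The check has two parts: what the two margins can identify, and whether another planned output supplies what is missing.

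**What the margins identify.** Let N be the number of subjects with both values, b the number above the ULN at baseline, and W the number above it at worst postbaseline. The count moving from at or below the ULN to above it lies between max(0, W − b) and min(W, N − b). Dividing by N − b gives the range for the new-elevation rate.

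Inputs: N = 22 is the maximum enrolled per Phase 2 cohort (SAP section 4). W = 13 and the values of b are assumptions, used only to show the mechanism. The displayed postbaseline percentage is 13/22 = 59.1% throughout.

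| b | Lowest possible rate | Highest possible rate | Difference from 59.1% (points) |
|---|---|---|---|
| 0 | 13/22 = 59.1% | 13/22 = 59.1% | 0 |
| 2 | (13 − 2)/(22 − 2) = 11/20 = 55.0% | 13/20 = 65.0% | −4.1 to +5.9 |
| 4 | (13 − 4)/(22 − 4) = 9/18 = 50.0% | 13/18 = 72.2% | −9.1 to +13.1 |

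With b = 0 there is no problem. If every subject who enters above the ULN has at least one later value above it, the rate is (W − b)/(N − b), the lower figure, and can be worked out from the two displayed margins. The upper figure requires all of those subjects to stay at or below the ULN at every later test.

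**Whether another output fills the gap.**

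- *Change from baseline by visit (SAP section 5.6.3).* This shows the size of change, not whether the ULN was crossed.
- *Chemistry shift table (SAP section 5.6.3.1).* It covers all clinical chemistry parameters, but by CTCAE grade. The documents give no grade for TSH, and section 5.6.3.2 uses a ULN split instead.
- *Hypothyroidism as a CSAE (SAP section 5.6.2).* The plan includes "Incidence and Time to First Onset of CSAEs for lenvatinib and AEOSI for everolimus", which depends on adverse event reporting. Protocol section 9.5.1.5.1 admits as an adverse event "Any unfavorable and unintended sign (including an abnormal laboratory finding), symptom, or disease temporally associated with the use of an investigational product" and requires that status when a laboratory abnormality leads to intervention. It also says "Medical and scientific judgment should be exercised in deciding whether an isolated laboratory abnormality should be classified as an AE". An untreated, isolated TSH rise may or may not appear.
- *Listings.* Under SAP section 5.6.3, "Laboratory test results will be assigned a low/normal/high (LNH) classification", and abnormal values are flagged in listings. Section 5.6.3.1 adds "All hematology and clinical chemistry laboratory parameters will be listed by subject and visit". The count can therefore be made by hand, but it is not tabulated.

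**The case against.** The strongest reply is that the parent section already covers this. SAP section 5.6.3 and Protocol section 9.7.1.8.3 promise shift tables from baseline to worst postbaseline for qualitative parameters, and section 5.6.3.2 turns TSH into a two-level category at exactly those two time points. A programmer might cross-tabulate on that basis. The table shells are also in a separate document (SAP section 11) and could show a two-by-two layout. This reading is arguable. However, TSH is measured quantitatively and has its own sentence, and that sentence calls for separate summaries. Shells that cannot be seen cannot be assumed to override it.

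A second reply is that silence on a CTCAE grade for TSH proves little, since the protocol reproduces no test-specific grading at all. That is correct, so how TSH would be handled in the chemistry shift is uncertain. Even so, a shift by grade is not stated to be a shift across the ULN.

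The third reply concerns size, and much of it stands. Worst postbaseline is taken over tests at every cycle, so a subject who enters high needs only one later high value to remain in the upper category. In that case the margins suffice. Treated hypothyroidism should be captured as an adverse event, and the treatment-emergent definition already accounts for baseline status. In a cohort of at most 22, counting from listings is easy. The ranges above are mathematical bounds on assumed counts, not estimates of distortion. These points limit the importance of the finding without removing it.

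**Conclusion.** The concern holds. As written, SAP section 5.6.3.2 produces two margins that do not, in general, identify how many subjects rose above the ULN on treatment, and no other planned summary table clearly supplies that count. The conclusion rests on the wording of that section, because the shells were not available. It has practical effect only if some subjects enter above the ULN, which the eligibility criteria permit but the documents do not quantify. The consequence is confined to one descriptive safety table.

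**What to change.** Replace the two separate summaries in SAP section 5.6.3.2 with a shift table of baseline category (at or below ULN, above ULN) against worst postbaseline category, by dose level in Phase 1 and by cohort in Phase 2. Report the proportion above the ULN postbaseline among subjects at or below it at baseline. Use subjects with both values as the denominator, in line with the paired-results rule in section 5.6.3. On that denominator the two summaries now planned remain as the row and column totals, so nothing is lost.

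The cost is reprogramming one table from data already collected, in the shift format the SAP already uses for proteinuria and other safety measures. There is no real downside.

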5.6.3.3 Urinalysis

The shift of Baseline to worst postbaseline proteinuria will be summarized. All urinalysis parameters (RBCs/high-power-field [HPF], blood, glucose, and protein [dipstick], 24-hour urine protein) will be provided by subject listing at each visit.

5.6.3.4 Vital Signs

Vital signs will be summarized by assessment time and dose level for Phase 1 or study cohort for Phase 2 for the actual value and change from Baseline. Baseline will be defined as the last nonmissing result prior to the first administration of study drug.

Vital sign values will be evaluated on an individual basis by subject. Descriptive statistics for vital sign parameters (systolic [SBP] and diastolic [DBP] blood pressure (subjects $<$ 18 years old presented as percentile, other subjects \geq 18 years old presented in mmHg), heart rate, respiratory rate, body temperature, height, weight and BSA), as well as changes from Baseline, will be presented for each cycle and day.

Percentiles for height measurements will also be summarized using a shift table of lowest postbaseline from Baseline measurement by categories (5th, 10th, 25th, 50th, 75th, 90th, 95th).

Percentiles for BP values (only for subjects $<$ 18 years old [see Protocol Appendix 7 and 8]) will also be summarized using a shift table of worst postbaseline from Baseline measurement by categories ($<$ 90th percentile, 90th to 95th percentile, 95th to $<$ 99th percentile, SBP or DBP \geq 99th percentile). The overall percentile is taken as the worse of SBP/DBP percentiles.

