- Any Grade 3 or greater non-hematological toxicity attributable to the investigational drug with the specific **exclusion** of:
 - Grade 3 nausea and vomiting <3 days duration
 - Grade 3 diarrhea <3 days duration
 - Grade 3 weight loss
 - Grade 3 liver enzyme elevation, including ALT/aspartate aminotransferase (AST)/ gamma glutamyl transferase (GGT)/ bilirubin/alkaline phosphatase that returns to Grade ≤ 1 or baseline within 7 days
 - Grade 3 asymptomatic elevation in amylase or lipase that returns to Grade ≤ 1 or baseline within 7 days
 - Grade 3 elevation in triglycerides that returns to Grade ≤ 1 or baseline within 7 days
 - Grade 3 or 4 fever <5 days duration
 - Grade 3 infection <5 days duration
 - Grade 3 hypophosphatemia, hypokalemia, hypocalcemia or hypomagnesemia responsive to oral supplementation
 - Grade 3 proteinuria (UPC) ratio >1.9 unless confirmed with a second measurement within 72 hours
 - Grade 3 headache <3 days duration responsive to optimal management.

- Any Grade 2 non-hematological toxicity that persists for ≥ 7 days and is considered sufficiently medically significant or sufficiently intolerable by subjects despite optimal supportive care that it requires treatment interruption.
- Any dose interruption or reduction due to toxicity which results in administration of less than 75% of the planned dosage of lenvatinib and/or everolimus.
- Note: Allergic reactions that necessitate discontinuation of study drug will not be considered a DLT.
- **Dose-limiting hypertension:**
 - Any Grade 4 hypertension

Confirmed systolic or diastolic BP more than 25 mmHg above 95th percentile for sex, age, height/length, or an elevated diastolic BP (ie, >95th percentile for age) not controlled by a single antihypertensive medication within 14 days of use. An antihypertensive tablet or capsule that contains up to 2 antihypertensive ingredient medications will be considered a single antihypertensive medication.

B. Hematological DLT:

- In subjects evaluable for hematological toxicity, DLT is defined as:
 - Grade 4 thrombocytopenia (platelet count $< 25,000/\text{mm}^3$) or Grade 4 neutropenia, not due to malignant infiltration.
- Any \geq Grade 2 arterial thromboembolic events (including cerebrovascular ischemia, peripheral or visceral arterial ischemia).
- Note: Grade 3 or 4 febrile neutropenia will not be considered a DLT.

All DLTs must be reported to the sponsor within 24 hours of their occurrence.

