9.7.1.8.4 VITAL SIGNS

Descriptive statistics for vital signs parameters (ie, systolic and diastolic BP, pulse, respiratory rate, temperature, weight) and changes from baseline will be presented by visit. A shift table of hypertension from baseline to worst post-baseline grades will be provided.

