Appendix 7 Blood Pressure Levels for Boys by Age and Height Percentile

AGE (Year)	BP Percentile	Systolic BP (mmHg)							Diastolic BP (mmHg)						
		Percentile of Height							Percentile of Height						
	↓	5th	10th	25th	50th	75th	90th	95th	5th	10th	25th	50th	75th	90th	95th
1	50th	80	81	83	85	87	88	89	34	35	36	37	38	39	39
	90th	94	95	97	99	100	102	103	49	50	51	52	53	53	54
	95th	98	99	101	103	104	106	106	54	54	55	56	57	58	58
	99th	105	106	108	110	112	113	114	61	62	63	64	65	66	66
2	50th	84	85	87	88	90	92	92	39	40	41	42	43	44	44
	90th	97	99	100	102	104	105	106	54	55	56	57	58	58	59
	95th	101	102	104	106	108	109	110	59	59	60	61	62	63	63
	99th	109	110	111	113	115	117	117	66	67	68	69	70	71	71
3	50th	86	87	89	91	93	94	95	44	44	45	46	47	48	48
	90th	100	101	103	105	107	108	109	59	59	60	61	62	63	63
	95th	104	105	107	109	110	112	113	63	63	64	65	66	67	67
	99th	111	112	114	116	118	119	120	71	71	72	73	74	75	75
4	50th	88	89	91	93	95	96	97	47	48	49	50	51	51	52
	90th	102	103	105	107	109	110	111	62	63	64	65	66	66	67
	95th	106	107	109	111	112	114	115	66	67	68	69	70	71	71
	99th	113	114	116	118	120	121	122	74	75	76	77	78	78	79
5	50th	90	91	93	95	96	98	98	50	51	52	53	54	55	55
	90th	104	105	106	108	110	111	112	65	66	67	68	69	69	70
	95th	108	109	110	112	114	115	116	69	70	71	72	73	74	74
	99th	115	116	118	120	121	123	123	77	78	79	80	81	81	82
6	50th	91	92	94	96	98	99	100	53	53	54	55	56	57	57
	90th	105	106	108	110	111	113	113	68	68	69	70	71	72	72
	95th	109	110	112	114	115	117	117	72	72	73	74	75	76	76
	99th	116	117	119	121	123	124	125	80	80	81	82	83	84	84
7	50th	92	94	95	97	99	100	101	55	55	56	57	58	59	59
	90th	106	107	109	111	113	114	115	70	70	71	72	73	74	74
	95th	110	111	113	115	117	118	119	74	74	75	76	77	78	78
	99th	117	118	120	122	124	125	126	82	82	83	84	85	86	86
8	50th	94	95	97	99	100	102	102	56	57	58	59	60	60	61
	90th	107	109	110	112	114	115	116	71	72	72	73	74	75	76
	95th	111	112	114	116	118	119	120	75	76	77	78	79	79	80
	99th	119	120	122	123	125	127	127	83	84	85	86	87	87	88
9	50th	95	96	98	100	102	103	104	57	58	59	60	61	61	62
	90th	109	110	112	114	115	117	118	72	73	74	75	76	76	77
	95th	113	114	116	118	119	121	121	76	77	78	79	80	81	81
	99th	120	121	123	125	127	128	129	84	85	86	87	88	88	89
10	50th	97	98	100	102	103	105	106	58	59	60	61	61	62	63

AGE (Year)	BP Percentile	Systolic BP (mmHg)							Diastolic BP (mmHg)						
		Percentile of Height							Percentile of Height						
	↓	5th	10th	25th	50th	75th	90th	95th	5th	10th	25th	50th	75th	90th	95th

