Appendix 8 Blood Pressure Levels for Girls by Age and Height Percentile

AGE (Year)	BP Percentile	Systolic BP (mmHg)							Diastolic BP (mmHg)						
		Percentile of Height							Percentile of Height						
	↓	5th	10th	25th	50th	75th	90th	95th	5th	10th	25th	50th	75th	90th	95th
1	50th	83	84	85	86	88	89	90	38	39	39	40	41	41	42
	90th	97	97	98	100	101	102	103	52	53	53	54	55	55	56
	95th	100	101	102	104	105	106	107	56	57	57	58	59	59	60
	99th	108	108	109	111	112	113	114	64	64	65	65	66	67	67
2	50th	85	85	87	88	89	91	91	43	44	44	45	46	46	47
	90th	98	99	100	101	103	104	105	57	58	58	59	60	61	61
	95th	102	103	104	105	107	108	109	61	62	62	63	64	65	65
	99th	109	110	111	112	114	115	116	69	69	70	70	71	72	72
3	50th	86	87	88	89	91	92	93	47	48	48	49	50	50	51
	90th	100	100	102	103	104	106	106	61	62	62	63	64	64	65
	95th	104	104	105	107	108	109	110	65	66	66	67	68	68	69
	99th	111	111	113	114	115	116	117	73	73	74	74	75	76	76
4	50th	88	88	90	91	92	94	94	50	50	51	52	52	53	54
	90th	101	102	103	104	106	107	108	64	64	65	66	67	67	68
	95th	105	106	107	108	110	111	112	68	68	69	70	71	71	72
	99th	112	113	114	115	117	118	119	76	76	76	77	78	79	79
5	50th	89	90	91	93	94	95	96	52	53	53	54	55	55	56
	90th	103	103	105	106	107	109	109	66	67	67	68	69	69	70
	95th	107	107	108	110	111	112	113	70	71	71	72	73	73	74
	99th	114	114	116	117	118	120	120	78	78	79	79	80	81	81
6	50th	91	92	93	94	96	97	98	54	54	55	56	56	57	58
	90th	104	105	106	108	109	110	111	68	68	69	70	70	71	72
	95th	108	109	110	111	113	114	115	72	72	73	74	74	75	76
	99th	115	116	117	119	120	121	122	80	80	80	81	82	83	83
7	50th	93	93	95	96	97	99	99	55	56	56	57	58	58	59
	90th	106	107	108	109	111	112	113	69	70	70	71	72	72	73
	95th	110	111	112	113	115	116	116	73	74	74	75	76	76	77
	99th	117	118	119	120	122	123	124	81	81	82	82	83	84	84
8	50th	95	95	96	98	99	100	101	57	57	57	58	59	60	60
	90th	108	109	110	111	113	114	114	71	71	71	72	73	74	74
	95th	112	112	114	115	116	118	118	75	75	75	76	77	78	78
	99th	119	120	121	122	123	125	125	82	82	83	83	84	85	86
9	50th	96	97	98	100	101	102	103	58	58	58	59	60	61	61
	90th	110	110	112	113	114	116	116	72	72	72	73	74	75	75
	95th	114	114	115	117	118	119	120	76	76	76	77	78	79	79
	99th	121	121	123	124	125	127	127	83	83	84	84	85	86	87
10	50th	98	99	100	102	103	104	105	59	59	59	60	61	62	62
	90th	112	112	114	115	116	118	118	73	73	73	74	75	76	76
	95th	116	116	117	119	120	121	122	77	77	77	78	79	80	80
	99th	123	123	125	126	127	129	129	84	84	85	86	86	87	88

AGE (Year)	BP Percentile	Systolic BP (mmHg)							Diastolic BP (mmHg)						

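### In subjects under 18 the SAP summarises BP and its change only as percentiles, a scale too compressed at the top to measure the size of the BP effect across dose levels

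*SAP*

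**What the plan says.** SAP 5.6.3.4 opens by promising vital signs "for the actual value and change from Baseline". The sentence specific to BP then sets the scale: those under "18 years old presented as percentile, other subjects" in mmHg. The same sentence covers change: "as well as changes from Baseline, will be presented for each cycle and day".

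The only other summary of BP measurements in under-18s is a shift table in four percentile categories. Its top category is open-ended from the 99th percentile. The table takes one value per subject: "The overall percentile is taken as the worse of SBP/DBP percentiles".

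Protocol 9.1 defines one part of dose-limiting hypertension in mmHg: "Confirmed systolic or diastolic BP more than 25 mmHg above 95th percentile for sex, age, height/length". Grade 4 hypertension and an elevated diastolic pressure not controlled by one agent also count.

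Protocol 9.7.1.8.4 plans "Descriptive statistics for vital signs parameters (ie, systolic and diastolic BP" and other parameters, with no percentile restriction, plus a shift table by hypertension grade. SAP section 7 states that nothing departs from the protocol's planned analyses.

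Phase 1 enrols ages 2 to under 18 (Protocol 9.3.1). At least half of each Phase 2 cohort must be under 18 at consent (Protocol 9.1).

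**The concern.** A percentile is a rank in a reference population. It moves quickly per mmHg near the median and hardly at all in the tail. Lenvatinib's BP effect matters most in the tail, where the protocol itself turns to mmHg above the 95th percentile.

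A mean percentile change weights a modest rise near the median heavily and a large rise from an already high value lightly. It can therefore rank two groups in the opposite order to their mmHg changes. In Phase 1, where cohorts are small and all subjects enrol under 18, this is the only planned quantitative summary of BP measurements by dose level and cycle.

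**Working it through.** **Inputs.** The tables headed "Blood Pressure Levels for Boys by Age and Height Percentile" (Protocol Appendix 7) and "Blood Pressure Levels for Girls by Age and Height Percentile" (Appendix 8) give BP at the 50th, 90th, 95th and 99th percentiles. Their footnotes place the 90th, 95th and 99th at 1.28, 1.645 and 2.326 SD above the mean. The DLT limit is the 95th percentile + 25 mmHg.

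**The plan's own figures.** Standard normal quantiles at 0.90, 0.95 and 0.99 are 1.2816, 1.6449 and 2.3263. The footnotes are reproduced, so the appendices imply a normal model.

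**Gap in mmHg.** Gap = (95th + 25) − 99th. Over all 476 cells (2 sexes × 17 ages × 7 height columns × SBP/DBP), the 99th exceeds the 95th by 7 or 8 mmHg. The gap is therefore 18 or 17 mmHg in every cell. For ages 2 to 17:

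| Table | Gap 17 mmHg | Gap 18 mmHg |
|---|---|---|
| Boys SBP | 36 | 76 |
| Boys DBP | 100 | 12 |
| Girls SBP | 15 | 97 |
| Girls DBP | 46 | 66 |

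**The same gap in percentile points.** Implied SD = (99th − 95th)/(2.326 − 1.645):
- 7/0.681 = 10.28 mmHg. Limit at 1.645 + 25/10.28 = 4.08 SD, percentile 99.998.
- 8/0.681 = 11.75 mmHg. Limit at 1.645 + 25/11.75 = 3.77 SD, percentile 99.992.

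The gap is thus 0.992 to 0.998 points. If percentiles are read from the printed tables, whose top row is the 99th, it is 0.

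**Compared with a move near the median.** Boy aged 13, median height (Appendix 7): SBP 50th 108, 90th 122, 95th 126, 99th 133 mmHg. SD = (126 − 108)/1.645 = 10.94. DLT limit = 126 + 25 = 151.
- 108 to 118 (+10 mmHg): Φ(10/10.94) = 0.82, so 50 to 82, about +32 points.
- 133 to 151 (+18 mmHg): Φ(25/10.94) = 0.989 and Φ(43/10.94) = 0.99996, about +1.1 points. The excess over 1 comes from deriving the SD from rounded entries, which puts 133 at 98.9. Nothing above the 99th can move more than 1 point.
- 122 to 151 (+29 mmHg): 90 to 99.996, about +10 points.

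Both 108 and 122 lie below the 95th percentile, so both are eligible baselines. The rise of 29 mmHg scores about a third of the rise of 10 mmHg.

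A second case is a boy aged 10 of median height (50th 102, 95th 119, 99th 127, limit 144; SD = 17/1.645 = 10.33). The 17 mmHg above the 99th is 1.0 point. The same 17 mmHg above the median is Φ(17/10.33) − 0.5, or 45 points.

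**The case against.** The percentile is the protocol's own clinical scale for children (Protocol 9.4.1.2), and the 95th and 99th are its management thresholds (9.4.1.3). It also removes age and growth. Median-height 50th percentile SBP in boys is 88 mmHg at age 2 and 118 at age 17, a spread of 30 mmHg from age alone. A median-height boy going from 12 to 14 gains 5 mmHg (106 to 111). Raw mmHg means in small dose cohorts would partly reflect age mix. This stands. It is why the percentiles should stay, and why a z-score or distance from the 95th percentile should accompany mmHg change.

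Three stronger readings are tempting, and the documents do not support them.
- A reader might infer that severe rises are hidden. Hypertension is a clinically significant event for lenvatinib, summarised by CTCAE grade and dose level with time to onset (SAP 5.6.2). DLTs are listed by subject with reason, date and dosage (SAP 5.6.1.4). The shift table isolates everyone at or above the 99th percentile.
- A reader might infer that dose levels cannot be compared on BP, or that dose-finding is affected. They can be compared by grade and by shift category. DLTs are determined by the investigator and the sponsor's medical monitor, with the steering committee as needed (Protocol 9.1), not from this table. The mmHg limit is one of several hypertension criteria.
- A reader might infer that a subject who turns 18 on study has no computable change. The SAP never says the unit switches mid-study, and BP is recorded in mmHg (Protocol 9.5.1.5.4).

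Table shells are in a separate document (SAP section 11), so an mmHg listing cannot be excluded. A listing would not supply the missing summary.

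**Conclusion.** The point holds as a limitation of one safety summary. For under-18s, mean percentile change is the only quantitative summary of BP measurements that the SAP specifies. It gives about 1 point or nothing to the last 17 to 18 mmHg before the protocol's mmHg limit, against about 32 points for 10 mmHg at the median in the worked case. It can rank effects the wrong way round and so is unreliable for the size of the BP effect across Phase 1 dose levels. No endpoint, DLT call or MTD decision is affected.

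The 17 to 18 mmHg comes straight from the tables. The point values assume the normal model in the appendix footnotes, because SAP 5.6.3.4 gives no formula for a continuous percentile. Under table look-up the compression above the 99th is complete.

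Separately, SAP 5.6.3.4 restricts the unit and uses percentile categories where Protocol 9.7.1.8.4 plans unrestricted BP statistics and a hypertension-grade shift table. The statement of no change in SAP section 7 is not accurate on this point.

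**What to change.** In SAP 5.6.3.4, for subjects under 18:
- Keep the percentile summaries and the shift table.
- Add change from Baseline in mmHg for SBP and DBP.
- Add the z-score for age, sex and height, or the mmHg distance from the individual's 95th percentile.
- Add a top shift category for values more than 25 mmHg above the 95th percentile. This mirrors the protocol's existing limit and changes no DLT or treatment rule.

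Reconcile SAP 5.6.3.4 and section 7 with Protocol 9.7.1.8.4: either restore the hypertension-grade shift table and unrestricted BP statistics, or declare the departure and give the reason.

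The cost is a few extra tables from data already collected. The mmHg figures must be read with age mix and growth in mind.
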